## 12.7 Interim Analyses and Reporting

There are no plans to conduct an interim analysis and no criteria by which the study would be terminated early based upon statistical determination

## 12.8 Sample Size Justification

Sample size calculation is based on published results regarding response time for distance and near visual acuity, with high and low contrast.

To demonstrate noninferiority (margin = 0.5 seconds) as a one-tailed hypothesis with  $\alpha = 0.05$ , and using a common standard deviation of 0.456, 80% power can be attained with a sample size of 48 (12 per group). For a comparison using a 3:1 ratio, required sample sizes for 80% power are 24:8 (test:control).

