Subject population	Presbyopic subjects aged $\geq 38$ and $\leq 58$ years with normal eyes (other than correction for refractive error), whose habitual correction is either any MF contact lens (with a preference for Alcon Precision Profile Design wearers) with a LO or MED ADD (or equivalent to an ADD of max +2.00 D) or progressive addition lens spectacles. Wear of habitual correction must be at least 5 days per week and at least 6 hours per day.
	Planned number of subjects enrolled: ~ 60
	Required number of completed subjects: 48 (12 per group)
Key inclusion	Presbyopic subjects aged $\geq 38$ and $\leq 58$ years with normal eyes
criteria	(other than correction for refractive error), whose habitual
(See Section 8.1 for a	correction is either any MF contact lens (with a preference for
complete list of	Alcon Precision Profile Design wearers) with a LO or MED ADD
inclusion criteria)	(or equivalent to an ADD of max +2.00 D) or progressive addition
	lens spectacles. Wear of habitual correction must be at least 5 days
	per week and at least 6 hours per day.
Key exclusion	Monocular subjects or subjects fit with only one contact lens.
criteria	Known pregnancy or lactating. History of or planned refractive
(See Section 8.2 for a	surgery or irregular cornea in either eye.
complete list of	
exclusion criteria)	
· 	

TDOC-0055656 Effective

Page 17 of 59

Data analysis and	Planned Analysis	Planned Analysis			
sample size justification	To address the primary effectiveness objective, planned analysi summarized below:				analysis is
	Endpoint	Comparison	Statistica	al Method	
	Primary				
	Average transition time between distance and intermediate	MF lenses vs PALs		ized linear in = 0.5 se	
	No inferential testin	ng will be perfor	med for th	e safety aı	nalyses.
	Sample Size Justification				
Sample size calculation for the primary effectiveness expression (one-sided $\alpha = 0.05$ ) is summarized below:					dpoint
	Primary Endpoint	Assumptions		Power	N/group
	Average transition time between distance and intermediate	Common SD  NI margin =		80%	12
Key words	Presbyopic, multifocal				
Associated materials	Lubrication/re-wetting drops will not be permitted within 2 hours prior to study Visit 2.				

Page 18 of 59

Table 3–1 Schedule of Study Procedures and Assessments

	ALL SUBJECTS	MULTIFOCAL CONTACT LENS WEARERS	PROGRESSIVE ADDITION LENS SPECTACLE WEARERS	ALL SUBJECTS
Visit	Visit 1/	Visit 2/	Visit 2/	Unscheduled

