## 12.4 Effectiveness Analyses

This study	defines 1 primary,			
	All effectiveness evaluations will use the FAS as the primary analysis set.			
	analyses of the primary	will be		
conducted using the PP Analysis Set only if the number of subjects excluded from the PP				
Analysis S	Set exceeds 5% of the FAS.			

A sequential gatekeeping strategy will be used to control testing of multiple effectiveness endpoints. Therefore, the overall Type I error will be maintained at one-sided 0.05 with the following testing order:

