# 12.4.1 Analysis of Primary Effectiveness Endpoint(s)

The primary objective of this study is to demonstrate noninferiority in transition time between distance and intermediate with MF contact lenses compared to PALs. The primary endpoint is the average transition time, calculated from a maximum of 3 readings, recorded in seconds, during alternate viewing from distance (4 m) to intermediate (80 cm) and vice versa.

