## 12.4.1.2 Analysis Methods

A generalized linear model will be utilized to test these hypotheses, with a term for treatment (4 levels: AOHG MF, DT1 MF, DACP MF, and PAL). Difference between MF (pooling all 3 MF groups) and PAL and the corresponding one-sided 95% upper confidence limit (UCL) will be computed. Noninferiority in transition time will be declared if the UCL is less than 0.5. Furthermore, subsequent superiority will be declared if UCL is less than 0.

19-Oct-2018 Protocol - Clinical

2.0; Most-Recent; Effective; CURRENT TDOC-0055656 Page 52 of 59

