### 4.3 Statistical Methods for Effectiveness Analyses

#### 4.3.1 Primary Effectiveness Analyses

A mixed effect repeated measures model will be utilized to test these hypotheses, with a term for treatment (4 levels: AOHG MF, DT1 MF, DACP MF, and PAL). Within-subject correlation due to multiple observations per subject will be accounted for. Difference between MF (pooling all 3 MF groups) and PAL and the corresponding one-sided 95% upper confidence limit (UCL) will be computed. Noninferiority in transition time will be declared if the UCL is less than 0.5. Furthermore, if noninferiority is demonstrated, subsequent superiority will be tested and declared if UCL is less than 0. Otherwise, no further testing will be carried out on this endpoint.

Analysis of the mixed effect repeated measures model will be implemented in SAS. The pseudocode is provided below.

```
proc sort data = studydata;  
  by subject;  
run;
```

```
proc mixed data = studydata;  
  class subject lens;  
  model transitiontime = lens;  
  random subject;  
  repeated / subj = subject type = cs;
```

```
lsmeans lens;  
contrast 'Compare MF vs PALs' lens 1 1 1 -3;  
run;
```

Additionally, descriptive statistics will also be provided summarize:

- Average transition time for each individual MF lens group
- Average transition time for distance to intermediate viewing
- Average transition time for intermediate to distance viewing

[REDACTED]

[REDACTED]

[Redacted]

[Redacted]

[Redacted]

[Redacted]

[Redacted]

[Redacted]

[Redacted]

[Redacted]

[Redacted]

[Redacted]

[Redacted]

[Redacted]

[Redacted]

[Redacted]

[REDACTED]

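### Is the stated 80% power with 12 per group the wrong figure for a primary test that compares 36 multifocal wearers with 12 spectacle wearers?

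*Protocol*

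**What the plan says.** The Protocol synopsis (section 3) introduces a table with "Sample size calculation for the primary effectiveness" endpoint and enters 80% power and 12 per group. Under subject population it states "Required number of completed subjects: 48 (12 per group"). Protocol 12.8 and SAP 7 give the margin (0.5 s), the common SD (0.456) and a one-tailed alpha of 0.05, and conclude that "80% power can be attained with a sample size of 48 (12 per group"). The sentence that follows in both places gives a second requirement: at a 3:1 ratio of test to control, 24:8 is needed for 80% power.

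The primary analysis in Protocol 12.4.1.2 is the "Difference between MF (pooling all 3 MF groups) and PAL". SAP 4.3.1 codes it as "contrast 'Compare MF vs PALs' lens 1 1 1 -3". Single lenses appear in the readable primary analysis only as descriptive statistics ("Average transition time for each individual MF lens group"). The endpoint, by Protocol 12.4.1, "is the average transition time, calculated from a maximum of 3 readings, recorded in seconds". Protocol 12.4 adds that "A sequential gatekeeping strategy will be used to control testing of multiple effectiveness endpoints", but the testing order itself is not visible in the public version.

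**The concern.** The synopsis ties 80% power and 12 per group to the primary endpoint. With four groups of 12, the pooled contrast compares 36 with 12, and its power under the same inputs is well above 80%. Twelve per group is the answer to a 1:1 question, yet no 1:1 comparison is visible among the primary tests. Neither Protocol 12.8 nor SAP 7 states, in readable text, the true difference assumed or whether the SD refers to a subject's average or to a single reading.

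If the sizing had been done for the wrong comparison, the trial could have the wrong number of subjects, or a reader could misjudge how firm a noninferiority result is likely to be. A printed 80% and a recomputed 94% are far enough apart to justify checking.

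**Working it through.** **Inputs.** From Protocol 12.8 and SAP 7: margin 0.5 s, SD 0.456 s, one-sided alpha 0.05, target power 80%, 12 per group, and 24:8 at a 3:1 ratio. The contrast is from Protocol 12.4.1.2 and SAP 4.3.1. Two inputs are assumptions: a true difference d = 0, and 0.456 as the SD of a subject's average.

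**Formula.** SE = 0.456 × √(1/n_MF + 1/n_PAL). Noncentrality = (0.5 − d)/SE. Power is the probability that a noncentral t with that noncentrality exceeds the one-sided 5% critical value of t.

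**1. The plan's own sizes, d = 0.**

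| MF:PAL | SE (s) | Noncentrality | df | Power |
|---|---|---|---|---|
| 11:11 | 0.456 × √(2/11) = 0.194 | 2.571 | 20 | 79.9% |
| 12:12 | 0.456 × √(1/6) = 0.186 | 2.686 | 22 | 83.1% |
| 21:7 | 0.456 × √(4/21) = 0.199 | 2.512 | 26 | 78.9% |
| 24:8 | 0.456 × √(1/6) = 0.186 | 2.686 | 30 | 83.6% |

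Twelve per group is the smallest 1:1 size with at least 80%, and 24:8 is the smallest exact 3:1 size. The two agree with each other: 1/12 + 1/12 and 1/24 + 1/8 both equal 1/6, so the standard error is the same. Both printed figures are reproduced. A one-sided alpha of 0.025 would not reproduce them: the normal approximation then gives 14 per group, or 9 controls at 3:1.

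**2. The planned primary contrast.** Dividing the contrast 1 1 1 −3 by 3 gives the mean of the three lens means minus the PAL mean. With 12 per group its variance is SD² × (3 × (1/9)/12 + 1/12) = SD² × (1/36 + 1/12) = SD²/9. So SE = 0.456/3 = 0.152 s, noncentrality = 0.5/0.152 = 3.289, df = 48 − 4 = 44, and power = 94.4%. The normal approximation gives 95.0%, and 200,000 simulated trials give 94.5%.

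**3. Planned against required.** The 3:1 requirement printed in the plan is 24 + 8 = 32 subjects. The plan has 36 + 12 = 48, a surplus of 16 (16/32 = 50%). A reader of either section can see this without any power calculation.

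**4. The assumed difference.** With SD 0.456, 12 per group and 24:8 are both minimum sizes only for a true difference between −0.0007 and 0.022 s. The printed sizes therefore imply a value of about 0. Over that range the power at 36:12 runs from 94.5% down to 92.6%.

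**5. How far the reserve goes (36:12, df 44).** If MF is truly slower by 0.05 s, power is 89.8%; by 0.10 s, 82.8%; by 0.116 s, 80.0%; by 0.15 s, 73.3%. With d = 0, power falls to 80% at an SD of about 0.594.

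**6. If 0.456 were the SD of a single reading.** For three readings with within-subject correlation ρ, the SD of the mean is 0.456 × √((1 + 2ρ)/3). For an assumed ρ from 0.8 to 0.3 this is 0.425 to 0.333, and power at 36:12 is 96.7% to 99.7%. The smallest 1:1 size would then be 10 down to 7 rather than the printed 12, so this reading does not fit the plan's figures.

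**The case for a change.** The best case for the concern is that a sample size justification should name the comparison it serves and the difference it assumes. Here the synopsis puts 80% on the primary endpoint, while the only visible primary test has about 94% under the same inputs. No passage prints that figure. The reserve also matters, because the SD comes from published response times in visual acuity testing rather than from the 4 m to 80 cm transition task, and a true disadvantage of about 0.116 s would use the reserve up.

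Part of this stands. The readable text of Protocol 12.8 and SAP 7 does not give the assumed true difference, and nowhere is the power at 36:12 printed. The rest does not amount to a fault. Entering target power beside planned group size is ordinary practice in a synopsis table, and 80% is true as a minimum. In the public copy the assumptions cell of that table has lost its values, so what the row specified cannot be judged. The 12 per group may serve a further comparison in the testing order that is not visible, and material withheld from the public version cannot be counted as missing from the plan. The assumed difference can be recovered from the printed sizes (step 4). The sensitivity to a slower MF lens or a larger SD is a property of any noninferiority design, and here it starts from a position above the target.

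**Conclusion.** The concern does not hold. Both printed sizes are correct minimum sizes for 80% power, and they are consistent with each other. The sentence after the quoted one gives the requirement for the 3:1 allocation that the primary test uses, and the planned 36:12 exceeds it by 16 subjects. The difference between 80% and about 94% is the difference between target and achieved power, and it is in the conservative direction. Type I error, the decision rule and the number of subjects are unaffected.

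The 94% rests on a true difference of 0 and on 0.456 s being the SD of a subject's average. The printed sizes support both assumptions, but the readable text states neither. Adding the achieved power and the assumed difference would be a reporting preference and not the correction of an error.

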#### 13 DATA HANDLING AND ADMINISTRATIVE REQUIREMENTS

# 13.1 Subject Confidentiality

The Investigator must ensure that the subject's anonymity is maintained throughout the course of the study. In particular, the Investigator must keep an enrollment log with confidential identifying information that corresponds to the subject numbers and initials of each study participant. At the end of the clinical study, the Study Sponsor will collect a copy of the enrollment log *without any identifying subject information*. All documents submitted to the Study Sponsor will identify the subjects exclusively by number and demographic information. No other personally identifying information will be transmitted to the Study Sponsor.

The Study Sponsor may release anonymized study data to external researchers for purposes of future research directly related to the study objectives, or future research that is beyond the scope of the current study objectives. The Informed Consent Form explains this to study subjects. Anonymization means that all identifiable information will be removed from the dataset and all links to the subjects in the study will be removed. Anonymization of the data will maintain confidentiality of the subjects who participate in the study so that they cannot be identified by external researchers. The anonymized data set will contain records from all

Page 55 of 59

of the subjects in the current study, but the anonymization process might change the data set in some ways, so external researchers will be informed that they might not be able to duplicate some of the results from this study.

#### 13.2 Completion of Source Documents and Case Report Forms

The nature and location of all source documents will be identified to ensure that original data required to complete the CRFs exist and are accessible for verification by the site monitor, and all discrepancies shall be appropriately documented via the query resolution process. Site monitors are appointed by the Study Sponsor and are independent of study site staff.

If electronic records are maintained, the method of verification must be determined in advance of starting the study.

At a minimum, source documents include the following information for each subject:

- Subject identification (name, sex, race/ethnicity)
- Documentation of subject eligibility
- Date of informed consent
- Dates of visits
- Documentation that protocol specific procedures were performed
- Results of study parameters, as required by the protocol
- IP accountability records
- Documentation of AEs and other safety parameters (if applicable)
- Records regarding medical histories and the use of concomitant therapies prior to and during the study
- Date of study completion and reason for early discontinuation, if applicable

It is required that the author of an entry in the source documents be identifiable. Direct access to source documentation (medical records) must be allowed for the purpose of verifying that the data recorded on the CRF are consistent with the original source data.

Only designated individuals at the site will complete the CRFs. The CRFs must be completed at regular intervals following the clinical study visit schedule. It is expected that all data reported have corresponding entries in the source documents. The Principal Investigator is responsible for reviewing and certifying that the CRFs are accurate and complete. The only

2.0; Most-Recent; Effective; CURRENT

Page 56 of 59

subject identifiers recorded on the CRFs will be subject number, and subject demographic information.

#### 13.3 Data Review and Clarifications

A review of CRF data to the subject's source data will be completed by the site monitor to ensure completeness and accuracy. After the CRFs have been completed, additional data clarifications and/or additions may be needed as a result of the data cleaning process. Data clarifications are documented and are part of each subject's CRF.

## 13.4 Sponsor and Monitoring Responsibilities

The Study Sponsor will designate a monitor to conduct the appropriate site visits at the appropriate intervals according to the study monitoring plan. The clinical investigation will be monitored to ensure that the rights and well-being of the subjects are protected, the reported data are accurate, complete, and verifiable from the source documents, and the study is conducted in compliance with the current approved protocol (and amendments[s], if applicable), with current GCP, and with applicable regulatory requirements.

The site may not screen subjects or perform the informed consent process on any subject until it receives a notification from an appropriate Study Sponsor representative that the site may commence conducting study activities. Monitoring will be conducted periodically while the clinical study is ongoing. Monitoring methods may include site visits, telephone, written and fax correspondence. Close-out visits will take place after the last visit of the last subject at the site.

A Coordinating Investigator may be identified by the Study Sponsor to review and endorse the final study report. In cases where a Coordinating Investigator is engaged, the Study Sponsor will select the Coordinating Investigator based upon their experience, qualifications, active study participation, and their willingness and availability to take on this role.

# 13.5 Regulatory Documentation and Records Retention

The Investigator is required to maintain up-to-date, complete regulatory documentation as indicated by the Study Sponsor and the Investigator's files will be reviewed as part of the ongoing study monitoring. Financial information is to be kept separately.

Additionally, the Investigator must keep study records and source documents consistent with the terms of the clinical study agreement with the Study Sponsor. If the Investigator retires, relocates, or for any other reason withdraws from responsibility of keeping the study records, then the Study Sponsor must be notified and suitable arrangements made for retention of

Page 57 of 59

study records and source documents needed to comply with national and international regulations.

## 13.6 Quality Assurance and Quality Control

The Study Sponsor will secure agreement from all involved parties to ensure direct access to all study related sites, source data and documents, and reports for the purpose of monitoring and auditing by the Study Sponsor, and inspection by domestic and foreign regulatory authorities. Quality control will be applied to each stage of data handling to ensure that all data are reliable and have been processed correctly. Agreements made by the Study Sponsor with the Investigator/Institution and any other parties involved in the clinical study will be provided in writing as part of the protocol or as a separate agreement.

#### 14 ETHICS

This clinical study must be conducted in accordance with the ethical principles contained within:

- The Declaration of Helsinki, and in compliance with the ICH E6 GCP Consolidated Guideline, ISO 14155:2011, and the applicable US FDA 21 CFR Regulations.
- SOPs of the Study Sponsor and contract research organizations participating in the conduct of the clinical study and all other applicable regulations.
- Notifications and timelines for reporting protocol deviations should be based upon applicable Ethics Committee requirements

The Investigator must ensure that all personnel involved in the conduct of the study are qualified to perform their assigned responsibilities through relevant education, training, and experience. The Investigator and all clinical study staff must conduct the clinical study in compliance with the protocol. Deviations from this protocol, regulatory requirements and/or GCP must be recorded and reported to the Sponsor prior to database lock. If needed, corrective and preventive action should be identified, implemented, and documented within the study records. Use of waivers to deviate from the clinical protocol is prohibited.

Before clinical study initiation, this protocol, the informed consent form, any other written information given to subjects, and any advertisements planned for subject recruitment must be approved by an IRB/IEC. The Investigator must provide documentation of the IRB/IEC approval to the Study Sponsor. The approval must be dated and must identify the applicable protocol, amendments (if any), informed consent form, assent form (if any), all applicable recruiting materials, written information for subject, and subject compensation programs. The

2.0; Most-Recent; Effective; CURRENT

TDOC-0055656 Effective

Page 58 of 59

19-Oct-2018

IRB/IEC must be provided with a copy of the Package Insert, any periodic safety updates, and all other information as required by local regulation and/or the IRB/IEC. At the end of the study, the Investigator must notify the IRB/IEC about the study's completion. The IRB/IEC also must be notified if the study is terminated prematurely. Finally, the Investigator must report to the IRB/IEC on the progress of the study at intervals stipulated by the IRB/IEC.

Voluntary informed consent must be obtained in writing from every subject and the process shall be documented before any procedure specific to the clinical investigation is applied to the subject. The Investigator must have a defined process for obtaining consent. Specifically, the Investigator, or their delegate, must explain the clinical study to each potential subject and the subject must indicate voluntary consent by signing and dating the approved informed consent form. The subject must be provided an opportunity to ask questions of the Investigator, and if required by local regulation, other qualified personnel. The Investigator must provide the subject with a copy of the consent form written in a language the subject understands. The consent document must meet all applicable local laws and provide subjects with information regarding the purpose, procedures, requirements, and restrictions of the study, along with any known risks and potential benefits associated with the IP and the study, the available compensation, and the established provisions for maintaining confidentiality of personal, protected health information. Subjects will be told about the voluntary nature of participation in the study and must be provided with contact information for the appropriate individuals should questions or concerns arise during the study. The subject also must be told that their records may be accessed by appropriate authorities and Sponsor-designated personnel. The Investigator must keep the original, signed copy of the consent (file in subject's medical records) and must provide a duplicate copy to each subject according to local regulations.

The Study Sponsor assures that the key design elements of this protocol will be registered on www.clinicaltrials.gov as required by current regulations and, if applicable, other public databases as required by local country regulations. In addition, results of this study will be made publicly available on www.clinicaltrials.gov regardless of outcome as required by current regulations and, if applicable, in other public databases as required by local country regulations.

Page 59 of 59

